4.6 OBJECTIVE

The objective of this study is to randomize patients with rectal cancer for either open or laparoscopic surgery to assess the role of laparoscopic TME in the treatment of rectal cancer. The most important endpoint in this study is locoregional recurrence rate 3 years postoperatively. A multi-center, international trial, with participation of centers in Western Europe has been designed, according to the COLOR I trial.

5 STUDY DESIGN

This trial is a randomized, international, multi-center study comparing laparoscopic and conventional resection for rectal cancer. Patients will be accrued by the participating hospitals of the COLOR II study group. The COLOR II study group is an international group of surgeons with interest and expertise in laparoscopic and colorectal surgery. Since 1997 the COLOR I study group has performed and almost completed a large international randomized controlled trial comparing laparoscopic to open surgery for colon cancer. Many centers of the COLOR I study group will join the COLOR II study group.

The design involves allocation of all suitable consecutive patients with rectal carcinoma to either of the two procedures at a randomization ratio of 2:1, in favor of the laparoscopic procedure. Excluded are patients with a carcinoma treated by local resection and palliative resections. The trial will be stratified according to participating center, resection type, preoperative radiotherapy and sex.

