6 ENDPOINTS

6.1 PRIMARY ENDPOINT

- locoregional recurrence rate 3 years postoperatively

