10 RANDOMIZATION

Once eligibility has been established and patient details have been logged, the patient will be allocated to either laparoscopic or conventional operation. Randomization will be performed by computer at time of randomization. Randomization will be balanced and stratified by participating center, resection type, radiotherapy and sex. When patients are not subjected to the treatment modality as randomized, data will be analyzed on an "intention to treat basis" (once randomized, patients will not be excluded or changed groups because of conversion or type of resection).

Randomization for all centers will be done through internet:

www.color2.org (click "investigators")

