16.2 DEFINITIONS OF LOCOREGIONAL RECURRENCE

- rectal exam positive for rectal cancer
- positive MRI or CT
- positive cytology or histology of adenocarcinoma

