19 STATISTICAL CONSIDERATIONS

19.1 SAMPLE SIZE AND STATISTICAL ANALYSIS

Locoregional cancer recurrence rate of operated patients with cancer stages <IV after 3 years is currently about 10 %. The primary objective of the study is to show that laparoscopic surgery does not lead to an increased locoregional recurrence rate. Equivalence of both treatments is considered to be shown if the resulting two-sided 95% confidence limits of the difference in 3-yrs locoregional recurrence rates excludes a difference greater than 5%. At a randomization ratio of 2:1, and assuming a recurrence rate of 10% in each group, 850 laparoscopic patients and 425 open patients are required to have a power of 80% for this study.

All analyses will be carried out on an "intention to treat" basis: patients, whose randomized laparoscopic operation was converted to an open resection, will be analyzed in the laparoscopic group.

Eight weeks operative mortality, pathological resection margins and complication rates will be compared using the Chi-square test. Locoregional recurrence rate, disease free survival and overall survival will be compared between the two procedures using log-rank statistic, adjusted for center. Exploratory analysis of the prognostic effects of various baseline data will be done using multivariate Cox-regression. Analysis of the primary endpoint will be performed 1.5 - 2 years after inclusion of all patients.

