 2 resection with TME and preservation of the anus
 3 resection with TME without preservation of the anus (APR)
21. please specify level of distal transaction : cm
(distance between distal transaction & dentate line)
22. ureter stent : 0 no
 1 yes
23. presence of fibrosis considered to be due to radiation : 0 no
 1 yes
24. macroscopic metastases : 0 no
 1 liver
 2 peritoneal
 3 mesentery
 4 other :
25. macr. invasion adj. organs : 0 no
(if yes, please mention which organ) 1 yes please specify:
26. Degree of pelvic autonomic nerve preservation:
 1. Total preservation of autonomic nervous system. (hypogastric and pelvic preservation procedure)
 2. Bilateral preservation of parasympathetic nerve system with complete removal of the sympathetic system. (bilateral pelvic preservation procedure)
 3. Unilateral preservation of parasympathetic nerve system with complete removal of the sympathetic system. (unilateral pelvic preservation procedure)

COLOR II

Dept. of Surgery, QEII Health Sciences Centre
 [name]
 [name], Halifax, Nova Scotia
 Canada [name]
 [contact]
 [contact]

Date:**Procedure:** LAP / OPEN**Rand nr:****Doctor:**

27. if appropriate, reason for incomplete preservation:

1. tumor invasion
2. other :

28. length of incision : cm

29. location of incision : 0 none
 1 transverse right
 2 transverse left
 3 Pfannenstiehl
 4 other:

30. anastomosis : 0 no (stoma)
 1 handsewn
 2 circular stapler; size : mm
 3 other:

31. anastomosis configuration :

- | | | | | |
|---|--------------|--------------------------|-----------|--------------------------|
| 0 | no (stoma) | | | |
| 1 | end to end |  | ileostomy |  |
| 2 | end to side |  | ileostomy |  |
| 3 | side to side |  | ileostomy |  |
| 4 | side to end |  | ileostomy |  |
-
- | | | | | | |
|--|--|--------------------------|---------|--------------------------|----------------------|
| | |  | J-pouch |  | transverse colostomy |
| | |  | J-pouch |  | transverse colostomy |

31a. Type of stapler used to transect the rectum

- | | | | | | | |
|---|----------------|--------------------------|------|--------------------------|-------|---------------|

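### Section 5 excludes palliative resections without saying when, and the primary endpoint does not fix whether or when residual or unresected local tumor counts as an event.

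*Protocol*

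**What the plan says.** **Who is excluded.** Section 5 says: "Excluded are patients with a carcinoma treated by local resection and palliative resections". No time point is attached. Sections 3.2 and 3.5 describe the population by curative intent. Section 9.3 lists only two exclusions after randomization: no adenocarcinoma, and invasion of uterus or vagina found at operation. Section 10 says: "once randomized, patients will not be excluded or changed groups because of conversion or type of resection". Section 19.1 puts all analyses on an intention-to-treat basis. Section 9.5 sets up a register that also covers patients excluded after randomization and gives inoperability as an example reason. Appendix V (investigator site file) refers to patients excluded postoperatively.

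**What counts as the primary event.** Section 6.1 names the "locoregional recurrence rate 3 years postoperatively". Section 16.2 defines a locoregional recurrence by any of three findings: "rectal exam positive for rectal cancer", a positive MRI or CT, or positive cytology or histology. It requires neither a prior complete resection nor a tumor-free interval. Section 16.1 accepts death with cancer as evidence of recurrent disease; section 16.2 does not list it. Section 15.1 schedules yearly clinical examination and one pelvic CT or MRI, at three years, with other investigations on indication.

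**What the forms record.** Item 20 (procedure performed) has three codes, all completed resections. Item 109 (nature of recurrence) has no code for persistent disease. Item 55 does code tumor in the surgical margins, and item 50 records the circumferential distance. Section 13.4 describes the R classification as prognostically strong, but no form item collects it.

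**The concern.** Whether an operation proves palliative, because gross tumor is left or cannot be removed, may become known only in theatre or afterwards. It is then an outcome of the operation being compared. If such patients are dropped, or kept but never scored as locoregional events, an arm with more of them shows a lower locoregional rate for that reason alone. In a trial whose claim is that laparoscopy does not increase locoregional recurrence, an uncounted excess in the laparoscopic arm moves the result toward success.

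Two people following the protocol could handle the same patient differently. A site could apply section 5 and the section 9.5 register and exclude a patient found inoperable. An analyst applying sections 10 and 19.1 would keep that patient. Once the patient is kept, section 16.2 still does not say whether the residual tumor is an event on the day of surgery, an event when next demonstrated, or no event if the patient dies first.

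**Working it through.** **1. The exclusion texts side by side.**
- Section 5: palliative resections excluded, timing not stated.
- Section 9.3: two exclusions after randomization, neither of them this one.
- Section 9.5 and Appendix V: exclusion after randomization or surgery is foreseen, with inoperability as an example reason.
- Section 10: no exclusion for type of resection. Resection type is a stratification factor there, and items 14 and 20 code it as partial mesorectal excision, TME with the anus preserved, or APR. Palliative versus curative is a different attribute, separated only in item 111 for treatment of recurrence. Section 10 therefore does not clearly cover it.
- Section 19.1: intention to treat for all analyses.

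**2. A patient with gross pelvic tumor left at surgery.**
- Tumor later shown on examination, scan or biopsy: an event under 16.2, dated by that finding.
- Death with cancer before any such finding: recurrent disease under 16.1, no locoregional event under 16.2.
- No resection done: item 20 has no code, and item 55 has no specimen to describe.

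**3. Reproducing the plan's sample size.** Inputs from 19.1: the criterion "Equivalence of both treatments is considered to be shown if the resulting two-sided 95% confidence limits" of the difference "excludes a difference greater than 5" percentage points, and "assuming a recurrence rate of 10% in each group, 850 laparoscopic patients and 425 open patients are required to have a power of 80" percent. With 2:1 allocation:

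n(open) = (1.960 + 0.842)² × [0.10×0.90/2 + 0.10×0.90] / 0.05² = 7.849 × 0.135 / 0.0025 ≈ 424, so 848 laparoscopic and 1272 in total. At 850/425, SE = √(0.09/850 + 0.09/425) = 0.01782 and power = Φ(0.05/0.01782 − 1.960) = 80.1%. The plan's 850 + 425 reproduces.

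**4. Effect of uncounted residual tumor.** Assumption: true local failure, residual tumor included, is 15% laparoscopic and 10% open, exactly at the margin. The pass probability is

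P = Φ([0.05 − (p_L − p_O)]/SE − 1.960), SE = √(p_L(1−p_L)/n_L + p_O(1−p_O)/n_O).

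With everything counted, P = 2.5%. Let r_L and r_O be the uncounted residual proportions. Kept as non-events, the rates become 0.15 − r_L and 0.10 − r_O. Removed, they become (0.15 − r_L)/(1 − r_L) and (0.10 − r_O)/(1 − r_O), with n reduced to match.

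| r_L / r_O | Uncounted patients (lap / open) | Kept as non-events | Removed |
|---|---|---|---|
| 0 / 0 | 0 / 0 | 2.5% | 2.5% |
| 1% / 0 | 8.5 / 0 | 7.7% | 6.6% |
| 2% / 1% | 17 / 4.25 | 8.0% | 6.6% |
| 2% / 0 | 17 / 0 | 18.9% | 15.1% |
| 3% / 1% | 25.5 / 4.25 | 20.1% | 15.6% |
| 1% / 1% | 8.5 / 4.25 | 2.5% | 2.3% |
| 5% / 5% | 42.5 / 21.25 | 2.5% | 1.7% |

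Example, 1% / 0 kept: SE = √(0.14×0.86/850 + 0.09/425) = 0.01880; (0.05 − 0.04)/0.01880 − 1.960 = −1.428; Φ = 7.7%.

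**5. Power cost of counting these patients.** If the common rate becomes 11%, SE = √(0.0979/850 + 0.0979/425) = 0.01859 and power = Φ(0.05/0.01859 − 1.960) ≈ 77%. At 12% it is about 74%.

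**The case against.** The case against is substantial.

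- **Section 5 reads most naturally as a selection rule.** It pairs palliative with local resection, and 9.2 lists local excision as an exclusion before randomization. Sections 9.3, 10 and 19.1 all speak against later removal. A reader might infer that the protocol instructs sites to drop palliative resections after surgery; it does not. What remains is that no text fixes the timing, while 9.5 and Appendix V foresee late exclusion.
- **Section 16.2 does not exclude residual tumor.** A reader might infer that tumor left behind is never a primary event. The text does not support that: persistent tumor on examination, imaging or biopsy meets the definition, and investigations on indication are allowed. The gap is the missing event date and the patient who dies before any qualifying finding.
- **The forms are not blind to it.** Items 50 and 55 give the main inputs for R0 versus R1. Missing are a no-resection code, a persistent-disease code and a record of macroscopic residue.
- **Selection and surgery rules should make the problem uncommon.** Section 9.2 excludes T4 and margin-threatening T3 tumors. Section 12.2 provides for conversion when gross positive margins are seen, and converted patients stay in the laparoscopic arm. This limits the likely size but does not decide how remaining cases are scored.
- **Event dating and sensitivity analyses may sit in an analysis plan that is not shown.** That is fair. The conflict over exclusion and the missing form codes, however, are in the protocol itself.

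**Conclusion.** The point holds as an ambiguity that should be resolved. It is not an error in a stated figure: the sample size reproduces. The protocol does not reconcile the section 5 exclusion with sections 9.3, 9.5, 10 and 19.1, and it does not fix whether or when gross residual or unresected local tumor enters the primary endpoint.

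The consequence is conditional. It requires more residual tumor in the laparoscopic arm than in the open arm, and those patients never being scored under 16.2 within three years. With true rates at the margin, an uncounted excess of 1 point raises the false-pass chance from 2.5% to about 7-8%. An excess of 2 points raises it to 15-19%, or 20.1% if the open arm also has 1% and patients are kept as non-events. Cases later detected reduce the uncounted excess. With equal residual rates there is no inflation. The protocol gives no residual-tumor rates, so every rate used here is an assumption. The documents therefore do not support the stronger inference that an operation leaving tumor behind improves its own locoregional result as a matter of rule.

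**What to change.** 1. In section 5, limit the exclusion to resections planned as palliative before randomization. Align 9.5 and Appendix V so that a patient found inoperable or palliatively resected after randomization stays in the intention-to-treat analysis.
2. In 16.2, count macroscopic local residual tumor, or an operation without resection, as a locoregional failure at the date of surgery. Add a sensitivity analysis that does not count these patients as events on that ground.
3. Add a no-resection code to item 20 and an R0/R1/R2 item to the case record form.

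The cost is amendment wording and two form changes. The endpoint becomes locoregional failure rather than recurrence in the strict sense. The event rate rises slightly, and power falls from 80% to about 77% if the common rate is 11% rather than 10%.

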6 ENDPOINTS

6.1 PRIMARY ENDPOINT

- locoregional recurrence rate 3 years postoperatively

6.2 SECONDARY ENDPOINTS

6.2.1 *Clinical*

- survival free of cancer recurrence at three, five and seven years
- overall survival at three, five and seven years
- distance of the tumor to the endopelvic fascia and the distal resection margin
- port-site and wound-site recurrences
- distant metastases rate
- 8-week or in-hospital operative mortality and morbidity
- macroscopic evaluation of the resected specimen

6.2.2 *Quality of life*

- duration of in-hospital stay postoperatively
- duration of absence of work
- postoperative health related quality of life (quality adjusted life years), including standardized questionnaires on sexual and bladder function

6.2.3 *Costs (national)*

- in hospital direct and indirect costs
- out-of-hospital postoperative costs

7 ETHICS

The trial must be approved by the appropriate ethics committee of each participating institution prior to its entry into the study. Eligible patients should be informed in person by the treating surgeon and receive written information about the trial in their own language. Informed consent should be obtained from each patient according to the guidelines of the local ethical committee, prior to randomization into the study. Patients remain free to withdraw at will at any time from the study without giving reasons.

To guarantee optimal treatment for patients in both treatment arms, interim analyses will be performed to compare survival and recurrence in both treatment arms. If differences of survival or recurrence rates are significant, accrual of patients will be stopped.

To assess the feasibility of laparoscopic rectal cancer resection, a phase II trial will precede the accrual of patients in this trial.

8 FEASIBILITY STUDY

The objective of the feasibility study is to control quality of laparoscopic TME procedures per center. Five consecutive laparoscopic TME's are performed, and either images are recorded or the procedure is observed by an expert in laparoscopic TME surgery. The protocol committee assigns laparoscopic TME experts per country. At least one recording of a laparoscopic TME has to be submitted to the monitoring committee for approval. The specimens of the 5 consecutive laparoscopic TME's will be examined both macroscopically and microscopically by the pathologist of the involved center as described below.

9 ELIGIBILITY

9.1 INCLUSION CRITERIA

- solitary rectal cancer observed at colonoscopy or on barium enema X-ray
- no evidence for distant metastases
- distal border of the tumor within 15 cm of the anal verge at rigid rectoscopy
- suitable for elective surgical resection
- informed consent according to local requirements

9.2 EXCLUSION CRITERIA (PRE-RANDOMIZATION)

- T1 tumor treated by local excision
- T4 tumors, staged prior to pre-operative chemo/radiotherapy
- T3 tumors with margins less than (<) 2mm to endopelvic fascia, by CT scan or MRI
- malignancy other than adenocarcinoma at cytological/histological examination
- patients under 18 yrs of age
- signs of acute intestinal obstruction
- more than one colorectal tumor
- Familial Adenomatous Polyposis Coli (FAP), Hereditary Non-Polyposis Colorectal Cancer (HNPCC), active Crohn's disease or active colitis ulcerosa
- scheduled need for other synchronous colon surgery
- preoperative indication of invasion of adjacent organs (immobile at palpation or CT/MRI showing invasion into surrounding structures)
- preoperative evidence of metastases (at least chest X-ray and ultrasonography of liver required to rule out metastases)
- other malignancies in medical history, except adequately treated basocellular carcinoma of the skin or in situ carcinoma of the cervix uteri
- absolute contra-indications to general anesthesia or prolonged pneumoperitoneum, such as severe cardiovascular or respiratory disease (ASA class > III)
- pregnancy

9.3 EXCLUSION CRITERIA (POST-RANDOMIZATION)

- no adenocarcinoma
- local invasion of uterus and/or vagina at operation

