9.5 NON INCLUDED & EXCLUDED PATIENTS

All patients suspected of having rectal cancer, who are considered for operation, should be registered. Thus patients who do not meet the inclusion criteria, as well as patients excluded after randomization, should be registered concerning date, hospital patient identification number, gender, location of tumor, type of operations, ASA class, TNM stage and Dukes stage. In addition to this registration, a short reason for non-

inclusion or exclusion should be noted.

For example:

- metastases
- inoperability
- no adenocarcinoma in resected specimen
- laparoscopic surgery contraindicated (include reason)

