12.2 CONVERSION

Conversion is defined as a change in operative approach to achieve the final goal and will be at the discretion of the individual surgeon for concerns of patient safety, technical difficulties, inability to complete the planned operation for sphincter sparing or associated conditions requiring treatment. Utilizing the extraction site for transverse stapler insertion to accomplish the distal anastomosis will not be considered a conversion. Identification of any grossly visible positive margins or extension into adjacent organs will mandate conversion to an open procedure. Completion of the pelvic dissection through open surgery will be considered conversion. Conversion is defined as a fascial incision longer than 10 cm, utilized to achieve anything other than specimen extraction. (Largest handport size is 8 cm)

13 HISTOPATHOLOGY.

All resected specimens are analyzed by the pathologist. Macroscopical assessment of the quality of mesorectal dissection will be scored in 3 grades.

- Complete: intact mesorectum with only minor irregularities of the mesorectal surface. No defect is deeper than 5 mm. No coning towards the distal margin of the specimen. Smooth circumferential resection margin on slicing.
- Partial incomplete: the majority of the mesorectum has been removed. Moderate coning of the specimen towards the distal margin. At no site is the muscularis propria visible with the exception of the area of the insertion of the levator muscles. Moderate irregularity of the circumferential resection margin.
- Incomplete: mesorectum with defects down onto muscularis propria and/or very irregular circumferential resection margin, coning.

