21.5 APPENDIX V: INVESTIGATOR SITE FILE

The investigator site file is made for each participating center. In this file all forms, lists and data concerning the COLOR II trial are stored. The contents of this file are listed below.

1. Registration form not included / excluded patients
All patients suspected of having a malignant rectal tumor, who do not meet the inclusion criteria or are excluded postoperatively, should be registered in this form.
2. Decoding list of patients
List of patients with randomization numbers and their corresponding hospital patient identification numbers. As only randomization numbers should be mentioned in the case record forms, this list is used to find patient files from trial patients if needed.
3. Decoding list of surgeons COLOR II trial
List of surgeons who operate on trial patients with their corresponding codes. Names of surgeons should not be mentioned in the case record forms.
4. Signed informed consent forms.
Copies cannot be sent to the coordinating center, because of privacy reasons.
5. Ethical committee approval & correspondence
6. Protocol & amendments
7. Copies of completed case record forms and follow up forms
Original completed forms should be sent to the coordinating center.
8. Monitor log & reports

[figure not shown]

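### Section 9.3 excludes randomized patients on findings made at or after the operation, which contradicts the intention-to-treat analysis in section 19.1 and can bias the primary comparison

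*Protocol*

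**What the plan says.** Protocol section 9.3 has two criteria that apply after randomization: "no adenocarcinoma" and "local invasion of uterus and/or vagina at operation". The first has no time point and does not name the tissue that decides. Section 9.5 gives "no adenocarcinoma in resected specimen" as an example reason for non-inclusion or exclusion.

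These patients are treated as outside the trial population. Section 9.5 asks that "patients excluded after randomization, should be registered concerning date, hospital patient identification number, gender, location of tumor" and a few further descriptors, plus a short reason. Appendix V keeps a separate form for patients who "do not meet the inclusion criteria or are excluded postoperatively". Neither place lists follow-up for them.

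Section 19.1 states: "All analyses will be carried out on an 'intention to treat' basis". It names no exception. Section 10 adds that "once randomized, patients will not be excluded or changed groups because of conversion or type of resection". Section 12.2 says that "extension into adjacent organs will mandate conversion to an open procedure".

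**The concern.** A trial cannot analyse everyone as randomized and also remove some randomized patients for what was found at or after surgery. The uterus/vagina finding is made during the allocated operation by a surgeon who necessarily knows the approach. It can arise only in women, and section 9.3 lists no other organ. Invasion of another organ is T4 disease in Appendix III, so these patients are plausibly at higher risk of locoregional recurrence.

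The stake is the primary claim in section 19.1, that laparoscopy does not increase 3-year locoregional recurrence. If the share excluded differs between arms and the excluded have a different prognosis, the observed difference is biased. If sites stop following these patients, a later analysis plan cannot bring them back, because the outcome will not exist.

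**Working it through.** **1. The passages side by side.** Take a woman in the laparoscopic arm whose uterine invasion is first seen at operation.
- Section 12.2: a mandatory conversion.
- Sections 10 and 19.1: a conversion stays in the laparoscopic group.
- Sections 9.3 and 9.5 and Appendix V: she is excluded and moved to the register.

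These cannot all be followed. In the open arm no conversion arises, but section 9.3 still conflicts with the unqualified statement in section 19.1.

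**2. The plan's own figure.** Inputs from section 19.1: 10% recurrence in each arm, 5-point limit, two-sided 95% interval (one-sided 0.025), 80% power, 2:1 allocation.
- n(open) = (1.960 + 0.842)² × (0.09 + 0.09/2) / 0.05² = 424. Laparoscopic is 848 and the total 1272, against 425 + 850 = 1275 stated. The figure reproduces.
- SE at 425/850 = √(0.09/425 + 0.09/850) = 0.01782. Power = Φ(0.05/0.01782 − 1.96) = 80.1%.

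The sample size is sound, but it contains no stated allowance for post-randomization exclusions.

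**3. Bias from unequal exclusion.** The protocol gives neither the share excluded nor their risk, so both are assumptions. If a share a is removed from an arm with true rate p, and the removed patients have risk r, the remaining rate is (p − a·r)/(1 − a).

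*Arms truly equal at 10%; 3% laparoscopic and 1% open excluded:*
- r = 0.30: 9.38% − 9.80% = −0.42 points.
- r = 0.40: 9.07% − 9.70% = −0.62 points.

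*True 5-point harm (15% laparoscopic, 10% open).* The false-claim rate is Φ((0.05 − d)/SE − 1.96), where d is the observed difference and SE uses the remaining rates and numbers. Without exclusions it is 2.5%.

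| Excluded, laparoscopic / open | r | d (points) | Shift (points) | False-claim rate |
|---|---|---|---|---|
| 3% / 1% | 0.30 | 4.74 | −0.26 | 3.4% |
| 3% / 1% | 0.40 | 4.53 | −0.47 | 4.4% |
| 1% / 0.5% | 0.30 | 4.95 | −0.05 | 2.7% |
| 1% / 0.5% | 0.40 | 4.90 | −0.10 | 2.8% |
| 2% / 2% | 0.30 or 0.40 | 5.10 | +0.10 | 2.2% |
| 3% / 1% | 0 (complete responders) | 5.36 | +0.36 | 1.6% |

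The direction depends on who is lost. Losing more high-risk laparoscopic patients favours laparoscopy. Losing more low-risk ones counts against it.

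**4. The histology criterion.** Biopsy is mandatory (section 11.1), non-adenocarcinoma malignancy is excluded before randomization (section 9.2), and preoperative radio- or chemotherapy is allowed (section 14.1). A patient with biopsy-proven cancer can therefore have a tumor-free specimen. Sections 9.3 and 9.5 as worded leave open whether she or he is excluded.

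If 5% of all patients were lost equally from both arms (assumption), 1275 × 0.05 ≈ 64 are missing and power is 78.1%. At 10%, about 128 are missing and power is 75.9%.

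**The case against.** Four objections have weight.

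- **The numbers are probably small.** Section 9.2 already removes T4 tumors, T3 tumors close to the endopelvic fascia and any preoperative indication of adjacent-organ invasion. Only occult invasion in women remains. If half the patients are women (assumption), 3% of an arm means 6% of its women, which looks high. This stands, and it is why the 1% / 0.5% row belongs beside the larger one.
- **Unequal detection is not documented.** Nothing in the protocol says that one approach reveals more uterine or vaginal invasion. The same rule applies in both arms, and randomization is stratified by sex. This stands: the bias is a possibility that the rule allows.
- **Section 10 does not itself forbid these exclusions.** Its ban covers conversion and type of resection only. This also stands. The contradiction rests on section 19.1, and on section 12.2 turning the same finding into a conversion.
- **The list in section 9.5 is only of examples and mixes non-inclusion with exclusion reasons.** Appendix III has a T0 category and section 13.4 allows R classification after multimodal therapy, so a tumor-free specimen can be classified within the trial. This stands as a caution on intent. The wording is still ambiguous.

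A reader might infer more than the text supports:
- That section 9.3 as a whole pushes towards a false finding of no harm. It does not: the two criteria can pull in opposite directions.
- That complete responders are definitely dropped. No passage says so.
- That invasion of every other organ stays in the analysis. Section 5 also excludes palliative resections, so some such cases may leave by that route.
- That the error rate at a true 5-point harm reaches 4.1–5.1% for the 3% / 1% split. That figure carries the equal-arms shift of 0.42–0.62 points over to a 15% against 10% truth. Recomputed there, the shift is 0.26–0.47 points and the rate 3.4–4.4%.

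**Conclusion.** The point holds as a contradiction in the protocol's text, and confidence in that part is high. Sections 9.3 and 9.5 and Appendix V remove randomized patients, apparently without follow-up, while section 19.1 promises intention to treat without exception.

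The effect on the result is possible but not demonstrated. On the assumed 3% / 1% split with 30–40% risk, the shift is 0.4–0.6 points when the arms are equal, and the false-claim rate is 3.4–4.4% instead of 2.5% at a true 5-point harm. On 1% / 0.5% it is 2.7–2.8%, and with equal shares and risks there is no inflation. The loss of power is minor: 78% to 76% if 5–10% of all patients are lost, against 80% planned. That loss depends on a reading of the histology criterion that the text permits but does not state.

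This should be fixed. The likely size does not put it among faults that invalidate the design.

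**What to change.** - State in sections 9.3 and 19.1 that all randomized patients are followed for the primary endpoint and analysed in their allocated arm in the primary analysis.
- Apply the uterus/vagina criterion only in a labelled sensitivity analysis.
- Limit the histology criterion to pre-treatment tissue obtained before randomization, and remove the resected specimen from section 9.5 as a reason for exclusion after randomization. Section 9.2 already covers most of this, so the restricted criterion would catch only patients randomized in error.
- Reconcile sections 9.3, 9.5, 10, 12.2 and 19.1 and Appendix V. The register can still record these findings, provided that follow-up continues. The conversion rule itself need not change for this purpose.

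The cost is protocol wording and follow-up of a few more patients, some with more advanced disease. The sample size stays at 1275 with 80.1% power.
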